6.2 Eligibility criteria

6.2.1 Inclusion criteria

- Clinical diagnosis of a Foot Ulcer, present on area that is measurable with a grid sheet (this can include plantar, calcaneus, dorsal, hallux, apex, or ankle based ulcers). This includes DFU, peripheral arterial disease related wound, or other aetiology.
- Minimum chronicity of 2 weeks applicable for the index foot ulcer.
- Adult patients aged ≥ 18 years
- Patients with recurrent wounds, including multiple wounds, are eligible. The largest of the wounds, that is measurable with a grid sheet, will be selected for the trial.
- Mental capacity to give consent

6.2.2 Exclusion criteria

- Under the age of 18 years
- Unable to fully understand the consent process and provide informed consent due to either language barriers or mental capacity
- Limited life expectancy, i.e. undergoing palliative care
- Active infection in foot ulcer that cannot be managed in podiatry service (ie requires specialist secondary care intervention)
- Ulcer penetrating the tendon, periosteum or bone, or a gangrenous or necrotic wound.
- Foot ulcer in area of the foot, e.g. in between toes, which would make exact ulcer size measurement, or application of the Natrox device, impossible.

- Currently receiving intravenous antibiotics, or within one week of receiving iv antibiotics (topical and oral antibiotics are not an exclusion criterion).
- Patients who are participating in another research study involving an investigational product that is related to the foot ulcer or a co-morbidity that may influence wound healing (incl. diabetes, peripheral arterial disease, or immune disorders).
- The patient has concurrent (medical) conditions that in the opinion of the investigator may compromise patient safety or study objectives, or significantly impede compliance with Natrox therapy.
- Any known reaction or hypersensitivity to the skin-facing component of the Natrox device, medical grade polyethylene.
- Ankle brachial index < 0.6, measured within 12 months of baseline visit (or recorded clinical opinion if calcification does not allow a reliable measurement).
- Use of barrier cream/ointment or honey-based dressing on the index wound itself

6.3 Subject withdrawal

6.3.1 Patient-driven early withdrawal and lost in follow-up

Patients have the right to withdraw from the trial at any time and without giving any reason. If a patient withdraws from the trial, any and all information gathered prior to the withdrawal will be excluded in the analysis, no further data collection will occur. If a patient does not attend a planned follow-up appointment then two more attempts will be made to contact the patient regarding the study. If still no contact can be made then the patient is deemed lost to follow-up and any collected study data will be retained. Since the study is not blinded, there is no requirement for an unblinding procedure.

6.3.2 **Intervention deviation**

Significant deterioration of index wound.

Clinical staff can stop Natrox treatment if they deem this to be clinically indicated. This is anticipated to be done only in cases where there is significant deterioration of the wound, not significant improvement. In cases of improvement the Natrox device is used until the wound is fully healed. The reason for discontinuing the Natrox therapy will be recorded, and participants will not be withdrawn from the study on that basis. This does not alter the study timelines and patients will continue to be followed up in accordance with planned study timepoints.

Examples are:

- Wound has become infected or critically colonised and treating podiatrist feels that intravenous antibiotics are indicated (see next paragraph).
- Deterioration in wound associated with increase in slough, which necessitates the use of a more absorbent dressing, and the Natrox device interferes with the dressing's usual mode of action.

Confidential – This document and the information contained herein may not be reproduced, used or disclosed without written permission from Cumbria Partnership NHS Foundation Trust Page | 17

- Deterioration in wound associated with increase in necrosis, which necessitates the use of a dressing that promotes hydration, and the Natrox device interferes with the dressing's usual mode ofaction.
- Adverse reactions to the Natrox device's 'web' element that touches the wound and surrounding skin will also be classed as a significant deterioration of the index wound in terms of subsequent wound management.

Even if Natrox therapy is discontinued, paarticipants will still be followed up at the indicated time points and asked to complete PROMs questionnaires, plus microbiology samples will be taken at the predetermined time points.

Use of intravenous antibiotics during trial

The use of topical or oral antibiotics is not an exclusion criterion and the initiation of said types of antibiotics does not necessitate withdrawal of the patient from the ANODE trial. However, the use of intravenous antibiotics specifically for the wound is an exclusion criterion. Therefore, if iv antibacterial treatment is required, the patient will be taken off Natrox treatment if they were allocated to that arm. Participants will still continue to be followed up to collate outcome measures in line with the protocol timelines. For participants in the treatment as usual arm the same approach will be taken, though there is obviously no requirement to withhold the Natrox treatment.

Study outcome measures will still be obtained where possible, in line with regular study timelines, and any reasons for Natrox therapy discontinuation will be recorded.

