5.3 Consent

Those eligible will be approached and provided with an information pack and consent form, which will be signed to indicate that informed consent has been given. Patients will be given ample time to consider taking part, more than 24 hours if they wish. The direct healthcare professional will first approach a patient about the study, and after verbal consent by the patient the healthcare professional themselves or a member of the research team can go through the informed consent process. If there is insufficient time in clinic, the podiatrist or delegated research can follow-up with a phone call to the patient to ensure they understand the PIS and have had opportunity to ask any questions they may have.

The start of the 4-week screening period is the date of written consent being obtained.

Participants will receive no incentives and consent will be regarded as a process and not a one-off event. Participants are free to withdraw from the study at any time without the need to give any reasons for withdrawal. Their standard of care will not be affected by either declining to participate in the study or withdrawing during participation. Data collected up to the date of withdrawal will be retained for analysis. Only one questionnaire will be presented to patients who withdraw or complete early, the patient experience questionnaire (still voluntary for patients to complete or not).

5.4 **Recruitment**

Participants will be enrolled for a total of 16 weeks, see Table 2, or until ulcer healing has been achieved (if the latter occurs then they will still be followed up according to the study schedule in terms of patient-reported outcome measures). All participants will have demographic and medical data obtained and a number of baseline and follow-up measures.

Table 2. Overview of study measurements

Weeks	-4	0*	3*	6*	9#	12~
Clinical characterization of wound	Х	Х	Χ	Х	Х	Χ
Ulcer size (Coloplast grid or suitable equiv)	Χ	Χ	Χ	Χ	Χ	Χ
PUSH score	Χ	Χ	Χ	Χ	Χ	Χ
SINBAD DFU grading score (DFU only)	Χ	Χ	Χ	Χ	Χ	Χ
Wound status (closed/recurrence/infection)		Χ	Χ	Χ	Χ	Χ
photo of wound (if possible and consented by patient)		Χ		Х		Х
QoL CWIQ		Χ		Χ		Х
QoL EQ-5D-5L		Χ		Х		Χ
Experience questionnaire (Natrox only)						Χ

^{*} Up to 1 week early or late

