5.6 Outcome measures

5.6.1 **Primary outcome measures**

To assess the feasibility of conducting a full CRT in the future, the primary outcome measures are mainly:

Trial-related outcome measures

- Participants' compliance to and satisfaction with Natrox device
- Recruitment and attrition rates, willingness of patients to be consented and randomised, response rates to questionnaires, and degrees of missing data
- Testing of eligibility criteria and ability/willingness of clinical staff to partake in recruitment of participants
- Ability of sites and clinicians to recruit and randomise patients
- To assess any training requirements
- Adequacy of duration of follow-up (e.g. in relation to foot ulcer healing)
- Fitness for purpose of data collection methods including across and between care settings
- Suitability of inclusion/exclusion criteria and outcome measure tools.
- Adverse events

5.6.2 **Secondary outcome measures**

This study also aims to record wound characteristics and patient-related outcomes measures, as well as safety endpoints and microbiology assessments.

The main clinical outcome for this trial will be the efficacy of the Natrox oxygen therapy in terms of wound healing. For all participants, wound healing will be measured

Foot ulcer size, measured with wound grid tool (week -4, 0, 3, 6, 9, 12). Measured in % change in cm² - between week 0 and weeks, 3, 6, 9, and 12 respectively

Assessment wound size and characteristics (wk 0,3,6,9,12)

- Clinical characterisation of wound (incl. erythema, purulence, odour), wound closure status
- PUSH and, if applicable, SINBAD DFU score

Extended safety outcome measures, general and in relation to applied Natrox (ongoing):

- Wound infection incidence
- Need for secondary interventions (incl. need for surgery, admission to hospital, iv antibiotics)
- (indirect) reaction to Natrox, the web itself or oxygen therapy
- Any other adverse events

Patient-reported outcome measures (wk 0, 6, 12)

- Quality of life score (EQ-5D-5L and Cardiff Wound Impact Questionnaire)

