6. SUBJECTS

6.1 Anticipated number of research subjects

This concerns a feasibility trial, and therefore the results from this study should inform a potential effect size for Natrox oxygen therapy, and also the degree in variance in wound healing rates (primary clinical outcome). To date, there is not sufficient published data to gain an insight in the effect that Natrox may have on foot ulcer healing. Hayes et al (2017) previously conducted a pilot study involving 10 DFU patients. In that study, there was no screening phase and Natrox treatment lasted for eight weeks. At the week 8 time point, a mean healing vs baseline of 51% was achieved.

Guidance from a publication by Julious (2005) advises the use of 12 participants per treatment arm, and this approach will be taken here (see Table 3). Patient withdrawal rates before week 12 are not known at present and measuring this will be a primary aim

Table 3, sample size numbers required, based on hypothetical differences between published data and study outcomes

	Standard (control) arm	care	Standard care plus Natrox oxygen therapy arm
Patients (n)	12		12

Since this concerns a randomised controlled trial, albeit in the shape of a feasibility study, reprting will be done in line with CONSORT guidelines (Schulz, Altman & Moher 2010). The number of patients screened but who did not meet the inclusion criteria or who declined to participate will be recorded, as will any patients who are lost to follow-up (Appendix 2).

Since this study involves a screening period, after which patients may not qualify for Natrox intervention, it is anticipated that more than 20 patients will be recruited. The patient attrition rate (withdrawal and loss to follow-up) will also be recorded, since this involves a study with at multiple visits, albeit incorporated into standard clinical appointments. Patients will be recruited from the adult (age 18+) population routinely seen by the evaluating clinical staff members.

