8.2 Primary outcome statistics

The primary objective for this pilot study is the feasibility of conducting a larger scale randomised controlled trial. The secondary outcome statistics (on efficacy) will aid to inform the success of this pilot study and will therefore inform whether a larger scale trial is indicated. This will be based on signs of clinical effectiveness, positive patient feedback on the intervention, positive changes in foot ulcer related quality of life, recruitment to time and target, low attrition rates, minimal data queries and lack of or low number of adverse events. If the effect size of the Natrox intervention pedal is large enough, then this pilot trial may possibly provide a definitive answer concerning its clinical effectiveness.

The following descriptive statistics will be reported on:

- Number of patients screened
- Number of patients eligible/ineligible, and percentage of patients consented into the trial

Number of patients completed the trial/discontinued (plus reasons if discontinued)

Patient feedback on the use and comfort of the Natrox device, and compliance with the prescribed therapy regime will be summarised in tabular and graph format.

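### Sections 5.3 and 6.3.1 give opposite rules for data collected before a patient withdraws; following 6.3.1 would take withdrawers out of primary feasibility and safety summaries

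*Protocol*

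**What the plan says.** Three current statements in the protocol govern the data of patients who leave early.

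- Section 5.3 (Consent), on withdrawal: "Data collected up to the date of withdrawal will be retained for analysis". It adds: "Only one questionnaire will be presented to patients who withdraw or complete early, the patient experience questionnaire", which is voluntary.
- Section 6.3.1, on withdrawal: "any and all information gathered prior to the withdrawal will be excluded in the analysis, no further data collection will occur".
- Section 6.3.1, on a patient who cannot be reached after two further attempts: "then the patient is deemed lost to follow-up and any collected study data will be retained".

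Other sections bear on what these rules affect. Section 5.6.1 lists among the primary outcomes compliance and satisfaction with the device, adverse events, and "Recruitment and attrition rates, willingness of patients to be consented and randomised, response rates to questionnaires, and degrees of missing data". Section 6.1 says: "Patient withdrawal rates before week 12 are not known at present and measuring this will be a primary aim". It also says: "The patient attrition rate (withdrawal and loss to follow-up) will also be recorded". Section 8.2 lists discontinuations, with reasons, among the descriptive statistics. It also bases the view on a larger trial partly on patient feedback, attrition and adverse events.

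**The concern.** The two withdrawal rules cover the same event and cannot both be applied. A statistical analysis plan could follow one only by departing from the other. The trial is unblinded (section 6.1.1), so if the choice is left until withdrawals have occurred, it may be made with results by arm in view.

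The rule in 6.3.1 is the damaging one. It has no exception for safety, compliance or experience data. It also makes inclusion depend on how a patient leaves: someone who states a decision to withdraw is removed from the analysis, while someone who stops attending is kept. A patient who leaves because the device is burdensome is informative about acceptability, and that patient's data would go. Control patients may withdraw too, but not over wearing the device, so the exclusion may be related to arm and to experience of treatment. The results at risk are those that section 8.2 uses to judge whether a larger trial is warranted.

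**Working it through.** No calculated figure in the protocol depends on this point. The only figure involved is the sample size: 12 + 12 = 24 randomised (section 6.1 and the protocol summary), which agrees.

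**Step 1. The two rules side by side, for a patient who withdraws between randomisation and week 12**

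| Item | Under 5.3 | Under 6.3.1 |
|---|---|---|
| Baseline data (8.1) | analysed | excluded |
| Wound size at weeks 3, 6, 9, if reached (8.3) | analysed | excluded |
| Week-12 wound size | not available | not available |
| Quality-of-life questionnaires already completed | analysed | excluded |
| Compliance data to date | analysed | excluded |
| Adverse events to date, in the analysis | analysed | excluded |
| Adverse event reporting to the sponsor (7.3) | done | done |
| Count of withdrawals (6.1, 8.2) | reported | reported |
| Experience questionnaire at withdrawal | offered | appears ruled out |

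The rules differ on everything the patient supplied before leaving. They do not differ on the week-12 measurement or on the count of withdrawals.

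**Step 2. Size per withdrawal**

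Input: 12 per arm. One withdrawal removes 1/12 = 8.3% of an arm, or 1/24 = 4.2% of all randomised patients, from the excluded items. Experience and device compliance come from the Natrox arm only, so 1/12 is the relevant share there.

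**Step 3. Range for an unknown rate**

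The protocol gives no withdrawal rate. Taking 10%, 20% and 30% of 24 as assumptions gives 2.4, 4.8 and 7.2 patients excluded.

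**Step 4. Two hypothetical cases in which the rules give different primary results**

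- *Missing data.* One of 12 Natrox patients withdraws after week 6 and the other 11 complete everything. With the withdrawer kept in the denominator, week-12 questionnaires are 1/12 = 8.3% missing. With the withdrawer excluded, they are 0/11 = 0% missing.
- *Adverse events.* Three of 12 Natrox patients have an event and two of those three withdraw. Under 5.3 the proportion is 3/12 = 25%. Under 6.3.1 it is 1/10 = 10%.

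These cases show the direction and scale that are possible. They do not predict what will happen.

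**The case against.** The strongest reply is that this is a wording slip with limited reach. The word for exclusion in 6.3.1 may be an error for inclusion, which would agree with 5.3. That is plausible, but the text does not show it, and a reader applying 6.3.1 as printed would exclude the data.

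Several safeguards stand. Section 6.3.2 keeps patients in follow-up when clinical staff stop the device, including after a reaction to the web, so such patients do not become withdrawals by default. Section 7.3 has all adverse events reported, assessed for causality and filed, with no exception for withdrawers. Attrition itself is still counted. These points narrow the problem to patients who choose to leave and to what is analysed, but they do not remove it: 6.3.1 makes no exception for adverse events in the analysis.

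The conflict over the questionnaire is the weaker part. A voluntary form handed over at the moment of withdrawal need not count as further collection. The two sections sit awkwardly together here rather than contradicting each other outright.

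A reader might infer stronger consequences that the protocol does not support:

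- *A loss of power or a shift in the week-12 healing rate.* A patient who withdraws before week 12 has no week-12 measurement under either rule, so a smaller week-12 sample is not caused by 6.3.1. A change such as 3/12 to 3/10 healed would require withdrawers to be counted as unhealed, which 5.3 does not say. The protocol states no power, and 12 per arm is a rule of thumb.
- *Destruction of data.* Section 6.3.1 concerns exclusion from analysis only.
- *A randomised comparison that is certainly invalid.* Informative exclusion is a risk that depends on how many patients withdraw and why, and neither is known.

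**Conclusion.** The contradiction is real and the protocol does not resolve it. As printed, 6.3.1 would take withdrawers' baseline, interim wound, compliance, questionnaire and adverse event data out of the analysis, while patients lost to follow-up keep theirs. Compliance, satisfaction, missing data and adverse events are primary outcomes, so this matters even though efficacy is secondary. The size is 8% of an arm per post-randomisation withdrawal. The total effect cannot be stated because the withdrawal rate is unknown.

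Bias in the device's favour is a risk, not an established effect. It rests on the assumption that some Natrox patients would withdraw because of burden or harm from the device.

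**What to change.** Replace the withdrawal sentence in 6.3.1 with the rule in 5.3: data collected up to the date of withdrawal, including adverse events, are retained and analysed in the arm to which the patient was randomised. State in both sections that the voluntary experience questionnaire is the only item offered at withdrawal and that nothing else is collected afterwards. Check that the consent form says the same. It is not among the documents reviewed, and Table 1 plans recruitment from October 2019, so patients may have consented before version 5.1 of January 2022.

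The cost is a change of a sentence or two, made as a protocol amendment that needs approval from the review bodies named in section 10.1. No visit, measurement or treatment procedure changes. The amendment should be made before the data are analysed by arm.

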7.2 Safety definitions

Adverse Event (AE)

Any untoward medical occurrence in a patient or other clinical investigation participant taking part in a trial of a medical device, which does not necessarily have to have a causal relationship with the device under investigation.

An AE can therefore be any unfavourable and unintended sign (including an abnormal laboratory finding), symptom or disease temporally associated with the use of the device, whether or not considered related to the device.

Serious Adverse Event

A serious adverse event is any untoward medical occurrence that:

- results in death
- is life-threatening
- requires inpatient hospitalisation or prolongation of existing hospitalisation
- results in persistent or significant disability/incapacity
- consists of a congenital anomaly or birth defect.

Other 'important medical events' may also be considered serious if they jeopardise the participant or require an intervention to prevent one of the above consequences.

NOTE: The term "life-threatening" in the definition of "serious" refers to an event in which the participant was at risk of death at the time of the event; it does not refer to an event which hypothetically might have caused death if it were more severe.

7.3 Procedures for recording adverse events

All AEs need to be reported to the sponsor/host Trust R&D within one week of the investigator team becoming aware of them. For this purpose an AE report form is completed by the researcher and/or Chief Investigator. SAEs should be reported within one working day of becoming aware of the event, where possible. The chief investigator and sponsor should be notified via this e-mail address: [contact]

The relationship of each adverse event to the trial must be determined by the Chief Investigator, a medically qualified individual, according to the following definitions:

- Related: The adverse event follows a reasonable temporal sequence from the Natrox oxygen device. It cannot reasonably be attributed to any other cause.
- **Not Related**: The adverse event is probably produced by the participant's clinical state or by other modes of therapy administered to the participant.
- **Severity grading**: the Chief Investigator will also record if it concerns an AE or SAE.

This is recorded on the aforementioned AE reporting form. The forms are stored in the study site file.

The participant's GP is informed of the adverse event. A copy of the adverse event form is sent to the GP along with a cover letter stipulating which patient it concerns. This will be done as soon as practically possible following completion of the AE form including causality reporting.

Pseudo-anonymised copies of all adverse events forms will be shared with Inotec AMD as soon as causality reporting has been performed and concluded.

